7.3.3 Study Procedure

Pulmonary vein (PV) isolation is the required ablation procedure. Additional optional ablation procedures are allowed based on clinical findings after the PV isolation is completed. Any non-PV foci identified in the left atrium (LA) and/or right atrium (RA) that trigger AF should be ablated. Isolation of the superior vena cava (SVC) should be performed if AF triggers are identified inside the SVC. Atrial linear lesions are allowed only if any arrhythmia is induced post PV isolation.

- In the US, several catheters are approved for the treatment of various cardiac arrhythmias. Only commercially available catheters that meet the specifications defined in this protocol may be used in this study. The subjects will be prepared, hemostatic introducers will be inserted, and anesthesia will be delivered per the standard protocol for the electrophysiology (EP) lab. A 30cm 14F femoral introducer sheath is recommended for introducing of the Artisan catheter.
- A single or double trans-septal puncture will be completed per standard EP lab protocol to access the left atrium.
- Systematic anticoagulation with heparin shall be administered per standard EP lab protocol with a recommended activated clotting time (ACT) of 300-400 seconds checked every 30 minutes.
- Evaluation of the location, morphology, and dimensions of each pulmonary vein by venogram or ultrasound may be performed at the discretion of the investigator. To evaluate the presence of intracardiac thrombus, TEE should be performed 24 hours prior to the procedure or the day of the procedure.
- Diagnostic catheters, such as coronary sinus and circular mapping catheters may be appropriately placed during the procedure at the discretion of the investigator.
- A routine EP study may be performed at the discretion of the investigator.
- Precautionary measures such as phrenic nerve pacing may be performed at investigator discretion prior to ablation.
- An esophageal temperature probe shall be placed to monitor esophageal temperature when ablating of the posterior left atrial wall.
- If the subject is in atrial fibrillation, cardioversion may be performed at the discretion of the investigator.
- A baseline structural echocardiogram (trans-thoracic, trans-esophageal, intra cardiac or IVUS) will be performed just prior to the introduction of the ablation catheter and a start time will be noted for the ablation portion of the procedure.
- If subject meets any of the intra-operative exclusion criteria, withdraw the subject from the study. The screening, baseline, and withdrawal case report forms should be completed. Any acute procedural adverse events shall be reported on the adverse event form.

- The ablation catheter shall be inserted into the Artisan catheter. If the ablation catheter does not fit smoothly through the Artisan catheter, the poorly fitting catheter should not be used and should be replaced with another catheter.
- Ablation of the cavotricuspid isthmus may be performed only in subjects with a history of typical atrial flutter or inducible cavotricuspid isthmus dependent atrial flutter.
- SVC isolation shall be performed if AF triggering potentials are noted in the SVC.
- The ablation catheter will be remotely manipulated to map and ablate within the atria.
 - The ablation catheter shall be placed within the Artisan catheter and manually introduced into the subject under fluoroscopic guidance.
 - A CARTO or EnSite Velocity three-dimensional electroanatomic mapping system shall be used to map the anatomical locations of pulmonary veins and ablative lesions.
 - A circumferential anatomical approach shall be used to electrically isolate the pulmonary veins.

Recommended Ablation Parameters:

Place ablative lesions 1-2 cm outside of the pulmonary veins in order to minimize the risk of pulmonary vein stenosis. Target Sensei® IntelliSense readings of 10-20g, with a maximum of 40g, during lesion creation.

RF power should typically be set to 20-25W with a nominal maximum power of 30W. Starting at 20-25W in an anatomical region, RF power may be increased after 15 seconds in 5W increments to achieve a transmural lesion as shown by local atrial electrogram attenuation or splitting. Ablation duration at a single anatomical lesion location is recommended to be limited to 30 seconds. If the ablation output time for the RF generator is set for longer than 30 seconds, the ablation catheter should be moved so that the ablation duration in a particular location doesn't exceed 30 seconds.

When ablating on the posterior left atrial wall, power should be reduced to mitigate the occurrence of an atrio-esophageal fistula. RF power should typically be set to 15-20W, and should not exceed 20W. Esophageal temperature should be monitored and energy delivery should be terminated if the esophageal temperature reaches or exceeds 41°C, as measured from the esophageal temperature probe.

Remember that stable contact between the catheter tip and the tissue increases the efficiency of RF power transfer to the tissue.

For power levels up to 30W, a flow rate of 17 ml/min should be used (refer to the catheter Instructions for Use for specific recommendations for flow rate). If the temperature increases to greater than 50°C or the impedance rises 20Ω or more, the RF application should be terminated

immediately, the ablation catheter should be removed and the coagulum removed (if present), and irrigation flow confirmed before the catheter is used again.

- Verification of electrical PV isolation: A circular or basket catheter shall be used for verification of PV isolation by demonstrating entrance block for each pulmonary vein. Confirmation of PV isolation in at least 3 of 4 pulmonary veins must be achieved to meet the criteria for acute procedural success.
- A second structural cardiac echocardiogram (trans-thoracic, trans-esophageal, intra cardiac or IVUS) will be performed five minutes after the ablation catheter is removed from the subject to assess for the presence of a pericardial effusion. The time of this evaluation will be documented.
- Refer to the Hansen Medical Artisan IFUs and the ablation catheter IFU for more catheter use information.
 - It should be recorded in case report forms if it is not possible to safely complete treatment of a pulmonary vein due to proximity of the phrenic nerve or esophagus.
 - Additional optional ablation lesions shall be noted (for example: mitral isthmus, cavo-tricuspid isthmus, or non-pulmonary vein foci).
 - For every RF energy application, the following ablation information will be collected: force, power, impedance value, temperature, irrigation flow rate, and ablation duration. Refer to the case report forms for specific items.

Post-Procedural Care:

- Subjects will be monitored in the recovery room until stable per the investigative site's standard post-treatment procedures.
- Low molecular weight or intravenous heparin should be used as a bridge to resumption of systemic anticoagulation following catheter ablation and sheath removal. All subjects should be on anticoagulation therapy for at least two months following the procedure. Decisions regarding the use of anticoagulation therapy for longer than two months following procedure should be based on the subject's risk factors for stroke and not the presence or type of AF. A CHADS₂ score will be used to determine the risk of stroke for the subjects and their need for anticoagulation therapy. Discontinuation of anticoagulation therapy beyond two months post ablation is not recommended in subjects who have a congestive heart failure, history of high blood pressure, age (75 years), diabetes, prior stroke or transient ischemic attack CHADS₂ score of ≥ 2 . Either aspirin or warfarin is appropriate for subjects with a CHADS₂ score of 1. Refer to **Appendix N** for the CHADS₂ score.

This anticoagulation strategy is based on the 2012 HRS Consensus Task Force recommendations, as listed on Table 4, Page 24 of the referenced HRS document.

- Each subject may be treated again using the Hansen System up to two more times during the blanking period.

- Any follow-up ablation procedure conducted within the study timeline for each patient, will need to be documented. The repeat ablation procedural date(s) and if the procedure was conducted manually or robotically will be the data points collected in the study database.
- Proton pump inhibitors should be administered for 4 weeks post ablation.

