Primary Endpoints	
Safety: The incidence of Major Complications, including the early onset (within 7 days of the ablation procedure) predefined complications; and the incidence of esophageal injury or pulmonary vein stenosis through day 180.
 
Effectiveness: Chronic Success is defined as:
 
 • Freedom from symptomatic atrial fibrillation (AF), atrial flutter, and atrial tachycardia episodes from days 91 - 365 after the initial ablation procedure, as documented by event recording, ECGs, and Holter monitoring. • No use of Class I, Class II, Class III or Class IV antiarrhythmic medications during days 91 - 365 after the initial ablation procedure with the following exceptions: 
 ▪ Addition of Anti- Arrhythmic (AAD) medication which was previously ineffective for AF and does not exceed the previous historical maximum dosage (24 hour total dose). ▪ Use of Atrioventricular (AV) nodal blocking agents such as beta blockers (BB) and/or calcium channel blockers (CCB) that are maintained at the current dose (does not exceed previous historical maximum dosage (24 hour total dose)). • No more than two additional ablation procedures within 90 days of the initial ablation procedure and no additional ablation procedures after day 90. • No use of a non-study device for ablation of any atrial fibrillation target. Commercially available non-study devices may be used for atrial flutter and atrial tachycardia ablation targets. • No ablation of an atrial fibrillation target made by removing the ablation catheter from the Artisan catheter and manually manipulating the ablation catheter. • Pulmonary vein isolation of at least 3 out of 4 veins confirmed by pulmonary vein entrance block during the last procedure within the blanking period. • No surgical ablation for atrial fibrillation, atrial flutter, or atrial tachycardia within 90 days of the study procedure.

	
 • No direct current (DC) cardioversion for atrial fibrillation, atrial flutter, or atrial tachycardia within days 91 - 365 after the initial ablation procedure. • No catheter or surgical ablation for atrial fibrillation, atrial flutter, or atrial tachycardia within days 91-365 after the initial ablation procedure.

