Medical Device	
Subjects will be treated with one of the specified commercially available RF ablation catheters within one of the family of Artisan guide catheters controlled by the Sensei® X Robotic Catheter System.
 
The ablation catheter shall be commercially available in the United States, and if used in Europe, the catheter shall be CE marked. The ablation catheter will be used per its instructions for use, although potentially outside its intended use.

Screening/Baseline	
 • Demographics • Medical history • Physical exam • NYHA Class • CT/MR within 3 months prior to initial ablation procedure to evaluate pulmonary veins and left atrial morphology and dimensions • 12-lead ECG • Labs, including CBC, BUN, serum creatinine (CR), INR*, pregnancy test • Anti-arrhythmic taken within the past 2 years; Anti-platelet or Anticoagulation medication taken within the past 3 months • Echocardiogram – Transthoracic Echocardiogram (TTE) / Transesophageal Echocardiogram (TEE) within 3 months prior to the index procedure to assess cardiac structure, function, LA size and EF • Echocardiogram – Transesophageal Echocardiogram (TEE) within 24 hours prior to the procedure to exclude left atrial thrombus 
Note: If preferred by the investigator, TEE or ICE within 24 hours or at the onset of the procedure for both structural and thrombus evaluations.

Intra/post-procedural Testing	
 • Cardiac echocardiogram prior to the introducing of the ablation catheter (e.g., TEE, TTE, ICE, or IVUS) • Cardiac echocardiogram 5 minutes after removal of the ablation catheter (e.g., TEE, TTE, ICE, or IVUS) • 12-lead ECG prior to leaving EP lab 
At Physician discretion the following may be performed:
 
 • Venogram or ICE to determine location, morphology and dimensions of each pulmonary vein • Routine EP study • Cardioversion • Phrenic nerve pacing • Esophageal temperature probe
Follow-up Testing	
Pre-Discharge:
 
 • 12-lead ECG • Serum creatinine, BUN, CBC

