- Concomitant medications (antiarrhythmic, anti-platelet or anticoagulation),
- 12-lead ECG,
- 24 hour Holter monitor,
- Cardiac CT or MR*,
- Major Complications,
- Adverse events.

Note: The safety CT/MR imaging must have the same Imaging parameters as the Baseline. For example, if a CT performed at baseline, a CT must be performed at this visit with the same imaging specifications.

365 days (\pm 30 days) post procedure

Subjects will be asked to return for a follow-up visit at 365 (\pm 30 days). At this follow-up visit, subjects will undergo an evaluation for changes in medications (anti-arrhythmic, anti-platelet or anticoagulation), Major Complications and adverse events. The following evaluations will be performed at this follow-up visit:

- Physical examination,
- NYHA classification,
- Concomitant medications (antiarrhythmic, anti-platelet or anticoagulation),
- 12-lead ECG,
- 24 hour Holter monitor,
- Major Complications,
- Adverse events,
- Cardiac CT or MR: *only required in subjects showing more than 50% narrowing of a pulmonary vein at the 180 day cardiac CT or MR imaging. The imaging modality and parameters must be the same as the initial baseline imaging.*
- Study Exit.

If at any time during the follow-up period a subject shows potential signs of pulmonary vein stenosis or atrio-esophageal fistula, the standard of care should be followed inclusive of the appropriate imaging for diagnosis. All reports of imaging done outside of the protocol required follow-up are to be forwarded to the Sponsor.

Table 9: Schedule of Study Assessments

	Screening/ Baseline (testing within 30 d)	Pre- Procedure (within 24 hrs.)	Procedure	Pre- Discharge	7-Day Follow-up (± 3d)	30 Day Follow-up (± 14d)	90 Day Follow-up (±14d)	180 Day Follow-up (± 30d)	365 Day Follow-up (± 30d)
Informed Consent	X								
Demographics and Medical History	X								
Physical Exam/Vital Signs	X			X		X	X	X	X
Medication History ¹	X			X	X	X ¹	X	X	X
Cardiac CT/MR*	X ⁸							X ¹¹	
12 lead ECG	X	X	X ⁹	X		X	X	X	X
NYHA Class	X					X	X	X	X
TEE/ICE		X ⁵							
TTE	X ¹⁰		X ⁶						
Esophageal temperature monitoring			X						
24 hr. Holter Monitor								X	X
Event Recorder (3 thru 12 months)							X ⁷	X	X
CBC	X			X					
BUN/Creatinine	X			X		X ⁴			
INR ²	X	X							
Pregnancy Test (within 7 days)		X ³							
Adverse Events			X	X	X	X	X	X	X
Device Performance			X						
Proton Pump Inhibitor Administration				X	X	discontinue			

1. Antiarrhythmic Anti-platelet, Anticoagulation

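### The protocol specifies the esophageal temperature probe inconsistently for posterior-wall ablation: discretionary in the synopsis, required in section 7.3.3, recommended in the ablation parameters, unconditional in Table 9

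*Protocol*

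**What the plan says.** Four places in the current protocol deal with esophageal temperature during the procedure.

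- **Synopsis, Intra/post-procedural Testing.** A list opens with "At Physician discretion the following may be performed" and its last item is "Esophageal temperature probe". No condition or exception is attached.
- **Section 7.3.3, procedure steps.** "An esophageal temperature probe shall be placed to monitor esophageal temperature when ablating of the posterior left atrial wall". The verb is mandatory, and the requirement is limited to one anatomical region.
- **Section 7.3.3, Recommended Ablation Parameters.** For posterior-wall work, monitoring is worded as *should*, and "energy delivery should be terminated if the esophageal temperature reaches or exceeds 41°C, as measured from the esophageal temperature probe".
- **Section 7.3.6, Table 9.** The row "Esophageal temperature monitoring" is marked in the Procedure column. It carries no footnote making it optional or limiting it to the posterior wall.

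The synopsis gives the primary safety endpoint as early Major Complications together with "the incidence of esophageal injury or pulmonary vein stenosis through day 180". Section 5.2 lists the esophageal component as atrio-esophageal fistula, from the procedure through 180 days.

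**The concern.** One precaution has four different standings: optional, required under a condition, recommended, and scheduled without condition. The 7.3.3 parameters present the posterior-wall precautions as mitigation against atrio-esophageal fistula, which counts toward the primary safety endpoint.

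Two things are at stake. First, the termination instruction depends on a reading "as measured from the esophageal temperature probe". An operator who took the synopsis at its word and placed no probe would have nothing to apply it to. Second, the trial is single-arm, runs at up to 14 sites and is judged against a fixed 16% safety goal. Section 6.8 bases pooling on sites using a common protocol. Text that allows two readings of a procedural safeguard weakens that premise, and it leaves a monitor without a clear basis for classifying an omitted probe.

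**Working it through.** No arithmetic applies. The point depends on no rate, margin, alpha or sample size, and the protocol states no figure that could be reproduced. The check is a comparison of the texts.

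**1. Can the synopsis and 7.3.3 both be followed?** Take a subject whose posterior left atrial wall is ablated. The synopsis leaves the probe to the physician, while 7.3.3 requires it. A physician who declines the probe complies with the first and breaches the second. The texts conflict for this case. For ablation elsewhere, these two texts do not conflict, because 7.3.3 is silent there.

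**2. Is the synopsis simply using looser language throughout?** Compare each item in its discretionary list with 7.3.3:

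- Venogram or intracardiac ultrasound of the pulmonary veins: discretionary in both.
- Routine EP study: discretionary in both.
- Cardioversion: discretionary in both (7.3.3 adds that it applies if the subject is in atrial fibrillation).
- Phrenic nerve pacing: discretionary in both; 7.3.3 reads "Precautionary measures such as phrenic nerve pacing may be performed at investigator discretion prior to ablation".
- Esophageal temperature probe: discretionary in the synopsis, mandatory in 7.3.3 for the posterior wall.

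Four of the five items agree and only the probe changes status. The synopsis list therefore tracks the body closely, and the mismatch is specific to the probe.

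**3. Is 7.3.3 consistent within itself?** Not fully. The procedure step uses *shall* for placing the probe. The later parameters use *should* for both the monitoring and the termination of energy, under a title that calls them recommended. Requiring a probe while only recommending that it be read and acted on is not strictly a contradiction, but it leaves the force of the requirement unclear.

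**4. Does Table 9 settle it?** No. It supports a scheduled assessment and so disagrees with the synopsis. It also drops the posterior-wall condition and so differs in scope from 7.3.3. Several other rows of that table carry qualifying footnotes; this row has none.

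**5. Is this superseded text?** No. The revision history in section 1.2 says esophageal temperature monitoring was added in a later Revision I. That might explain a synopsis that was not updated, but this is inference and the point does not need it. All four texts compared above are in the current revision.

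**6. Can the effect be sized?** No. The documents do not say what share of subjects will have posterior-wall ablation, how many operators would omit the probe, or how monitoring changes the risk of esophageal injury. Neither the 16% safety goal nor the 98% probability of study success stated in section 6.5 can be recalculated from what is given.

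**The case against.** The strongest case on the other side is that the body of the protocol governs and already contains what is needed. Section 7.3 directs the reader to the detailed descriptions of each time point. Section 7.14 defines a deviation as departure from the investigational plan as a whole, and section 13.3 says the protocol must be followed exactly. Section 9.1.1.1 provides protocol training and section 12.4 provides 100% monitoring. A site working from the synopsis alone is not the planned situation. One can also read the synopsis as a general list and 7.3.3 as a specific requirement for one region.

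Much of this stands, and it rules out several stronger readings that a reader might infer:

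- *That a site may omit the probe without a deviation.* Not supported. Omission during posterior-wall ablation departs from 7.3.3 whatever the synopsis says. The most that can be said is that a site could dispute the classification by pointing to the synopsis.
- *That the safeguard is being applied inconsistently.* The documents show inconsistent specification. Variation between sites is a risk and is not documented.
- *That every subject with posterior-wall ablation is affected.* This would require operators to follow the synopsis over 7.3.3, and nothing indicates how many would.
- *That the safety result is compromised.* The probe is not an endpoint assessment. Atrio-esophageal fistula is counted through day 180 and adjudicated by the Clinical Events Committee, and the 180-day visit looks for esophageal injury, whether or not a probe was used. Any effect could come only through an unquantified change in risk.

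The objection does not remove the conflict. The synopsis states no exception for the posterior wall, Table 9 states no condition, and the protocol sections cited here give no rule that the body prevails over the synopsis.

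**Conclusion.** The point holds as an internal contradiction in operative text. For posterior left atrial wall ablation the synopsis and section 7.3.3 are incompatible. The Recommended Ablation Parameters and Table 9 add two further standings, one advisory and one unconditional. The practical consequence is limited but real: a reader of the synopsis could omit the probe, be unable to act on the temperature-based termination instruction, and contest whether a deviation occurred.

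The size of any effect on event rates is unknown and cannot be derived from the protocol. The conclusion assumes only that the synopsis is part of the protocol that sites use, and that *may*, *shall* and *should* carry their ordinary meanings. It takes no position on which standing is clinically correct and does not call the endpoint definition, the performance goal or the analysis into question.

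**What to change.** Reconcile four places so that each states one requirement and the same condition for it: the synopsis list under Intra/post-procedural Testing, the procedure step in 7.3.3, the Recommended Ablation Parameters in 7.3.3, and the Table 9 row. If the requirement is limited to a region, say so in all four, for instance by a footnote in Table 9. The sponsor and its clinical advisers must decide what the requirement is.

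No new deviation rule is needed. Once the four texts agree, the existing definition in section 7.14 applies without ambiguity. The cost is a wording correction in the next amendment, with a check that site training material and case report forms match. No change to sample size, endpoint or analysis follows.

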5.3 Primary Effectiveness Endpoint

The primary effectiveness endpoint is chronic success. Chronic success is defined to be:

- Freedom from symptomatic atrial fibrillation, atrial flutter, and atrial tachycardia episodes from days 91 - 365 after the initial ablation procedure, as documented by event recording, ECGs, and Holter monitoring.
- No use of Class I, Class II, Class III or Class IV antiarrhythmic medications during days 91 - 365 after the initial ablation procedure with the following exceptions.
 - Addition of Anti- Arrhythmic (AAD) medication which was previously ineffective for AF and does not exceed the previous historical maximum dosage (24 hour total dose).
 - Use of Atrioventricular (AV) nodal blocking agents such as beta blockers (BB) and/or calcium channel blockers (CCB) that are maintained at the current dose (does not exceed previous historical maximum dosage (24 hour total dose).
- No more than two additional ablation procedures within 90 days of the initial ablation procedure and no additional ablation procedures after day 90.
- No use of a non-study device for ablation of any atrial fibrillation target. Commercially available non-study devices may be used for atrial flutter and atrial tachycardia ablation targets.
- No ablation of an atrial fibrillation target made by removing the ablation catheter from the Artisan catheter and manually manipulating the ablation catheter.
- Pulmonary vein isolation of at least 3 out of 4 veins confirmed by pulmonary vein entrance block during the last procedure within the blanking period.
- No surgical ablation for atrial fibrillation, atrial flutter, or atrial tachycardia within 90 days of the initial ablation.
- No direct current (DC) cardioversion for atrial fibrillation, atrial flutter, or atrial tachycardia within days 91 - 365 after the initial ablation procedure.
- No catheter or surgical ablation for atrial fibrillation, atrial flutter, or atrial tachycardia within days 91 - 365 after the initial ablation procedure.

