5.4 Secondary Endpoints

- **Acute Procedural Success**

Acute procedural success is defined as the successful ablation of at least three of four pulmonary veins as shown by pulmonary vein entrance block per vein during the initial ablation procedure. A subject is considered to be an acute procedural failure if acute procedural success cannot be obtained by using the Hansen system and, as a result, manual manipulation is needed to complete the ablation procedure with the ablation catheter.

- **Chronic Safety**

Chronic safety is defined as the incidence of Major Complications during the period from 8 – 365 days following the initial ablation procedure (excluding pulmonary vein stenosis and atrio-esophageal fistula from 8 – 180 days, which are included in the

primary safety endpoint). The incidence of pulmonary vein stenosis and atrio-esophageal fistula is included during the period from 181 – 365 days.

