6.4 Secondary Effectiveness Endpoint – Acute Procedural Success

The secondary effectiveness endpoint is acute success of remotely introducing and positioning of commercially available ablation catheter through the Hansen system. The secondary effectiveness endpoint is defined as the rate of acute procedure success for at least three out of four pulmonary veins as shown by pulmonary vein entrance block per vein during the initial ablation procedure. A subject is considered to be an acute failure if acute procedural success cannot be obtained by using the Hansen system and, as a result, manual manipulation was needed to complete the ablation procedure.

The rate is estimated using proportions per subject. A one-sided 95% lower confidence level will be calculated for acute success rate. No hypothesis test will be performed for this secondary effectiveness endpoint.

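### Section 5.3 scores re-treated subjects on entrance block and AF-target technique at the repeat, but section 7.3.3 lists just the date and a manual/robotic flag as repeat-procedure data

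*Protocol*

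**What the plan says.** Protocol section 5.3, with the same components in the synopsis, treats re-ablation as a planned route to success. The limit is "No more than two additional ablation procedures within 90 days of the initial ablation procedure", and none after day 90. A subject within that limit can be a chronic success if, among other things, isolation of at least three of four veins is "confirmed by pulmonary vein entrance block during the last procedure within the blanking period". Two further components concern technique. One is "No use of a non-study device for ablation of any atrial fibrillation target", with flutter and tachycardia targets exempt. The other fails a subject if an AF target is ablated by hand with the ablation catheter taken out of the Artisan catheter.

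Section 7.3.3, under Post-Procedural Care, allows up to two further treatments with the Hansen System in the blanking period and asks that any follow-up ablation be documented. It then names the data: "The repeat ablation procedural date(s) and if the procedure was conducted manually or robotically will be the data points collected in the study database".

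Earlier in 7.3.3, the general procedure steps call for entrance block to be checked in each vein and add: "Confirmation of PV isolation in at least 3 of 4 pulmonary veins must be achieved to meet the criteria for acute procedural success". The same steps ask that additional lesions be noted, and that the case report form record a vein that could not be treated safely. They also state: "For every RF energy application, the following ablation information will be collected: force, power, impedance value, temperature, irrigation flow rate, and ablation duration", and refer to the case report forms for details. Section 5.4 defines acute procedural success "as shown by pulmonary vein entrance block per vein during the initial ablation procedure", and section 6.4 does likewise: "three out of four pulmonary veins as shown by pulmonary vein entrance block per vein during the initial ablation procedure".

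**The concern.** For a re-treated subject, the last procedure within the blanking period is the repeat. Section 5.3 therefore judges vein isolation on what was found at the repeat, and the result from the initial procedure cannot stand in for it. Yet the one sentence that says what the database holds about repeats does not mention entrance block, the targets ablated or the device used.

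A required component of the primary effectiveness endpoint would then have no database entry for any subject re-treated by day 90, and two other components could be classified only in part. The trial has a single arm and is judged against a fixed goal of 54%. Any convention for handling the gap, whether generous or strict, moves the tested rate directly, with no control arm to absorb it.

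**Working it through.** No stated figure is in question, so the check sets each 5.3 component that a blanking-period repeat can affect beside what the listed repeat data can show.

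| Component in 5.3 | Needed from the repeat | Can date and mode settle it? |
|---|---|---|
| At most two repeats by day 90, none later | Date | Yes |
| Three of four veins isolated at the last blanking-period procedure | Entrance block per vein | No |
| No AF target ablated by hand outside the Artisan catheter | Manipulation mode by target | In part |
| No non-study device on an AF target | Device by target | In part |

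1. **Count and timing.** The dates give the number of repeats and show whether each fell before or after day 90. Any ablation after day 90 fails the subject, so the date is enough there. The gap is confined to blanking-period repeats.

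2. **Vein isolation.** Neither a date nor a manual/robotic flag carries information about entrance block. The acute-success assessment does not supply it, because 5.4 and 6.4 define that endpoint on the initial procedure. The list collected per energy application does not supply it either: its six items are force, power, impedance, temperature, flow rate and duration.

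3. **Technique.** The flag is set once per procedure, while 5.3 judges by target. A procedure done wholly robotically meets the manual-manipulation criterion. A repeat in which AF targets were ablated robotically and a flutter target by hand cannot be classified from one flag. A repeat flagged as manual could have treated AF targets, which is a failure, or non-AF targets alone, which is not. The flag also names no device, so it does not by itself show whether a non-study device was used, or on which target. The protocol treats the distinction as meaningful: 5.5 and 6.7 list non-AF targets ablated manually as an analysis.

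4. **The two readings of 7.3.3.** If the general verification step covers repeats, entrance block is obtained at each repeat and the repeat-data sentence is an incomplete list. If the step belongs to the initial procedure, as its link to acute success suggests, no passage asks for entrance block to be recorded at a repeat. On both readings 5.3 and the two parts of 7.3.3 need to be reconciled.

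**The case against.** The strongest reply is that the passages can be read together. The verification step stands in the general part of 7.3.3 with no restriction to the first procedure. The instruction to note additional lesions, and the planned analysis of non-AF targets ablated manually, are equally unrestricted. The repeat-data sentence covers every follow-up ablation during the study, including manual ones and those after day 90, for which date and mode suffice. It could be meant as a common minimum, and it does not contain the word only. The electronic case report forms (Appendix G) are not shown and may hold the missing items. Table 16 names forms for the index procedure but also has an open category for other forms, so it is weak evidence that no repeat form exists.

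Much of this stands. It weakens the AF-target half in particular, and it rules out saying that the data were not collected. It does not remove the conflict. The sentence says what will be the data points in the study database, and a site or database builder following it would not enter entrance block. An analysis plan cannot supply an item that was never entered.

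A reader might infer that re-treated subjects must be either credited without evidence or refused credit. The documents do not support that. Section 7.13 requires source records of the procedure, including logs and clinical findings. Section 12.4 requires 100% monitoring, and section 7.12 provides for querying missing data. The facts should usually be recoverable. The protocol also plans multiple imputation of missing final outcomes with a time-to-event model, but does not say whether that extends to a procedural finding such as entrance block.

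**Conclusion.** The concern holds as a conflict between 5.3 and two parts of 7.3.3. Taken literally, the repeat-data sentence leaves one required component of the primary effectiveness endpoint (entrance block at the repeat) outside the database for every subject re-treated in the blanking period, and leaves two components (manual manipulation and non-study device on an AF target) only partly classifiable. It should be fixed. Confidence is medium, because the case report forms are not at hand and the general steps may be meant to cover repeats.

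No effect on the trial result is claimed. A reader might want to work out how many uncredited re-treated subjects would reverse the effectiveness conclusion. That would be a tipping point for lost successes of any kind, not a measure of this problem. The protocol gives no expected share of re-treated subjects, and the prior is in Appendix M, which is not shown. Nor does the 100% acute success in Table 1 show that the criterion would be met at repeats: it pools each study's own definition and includes atrial flutter subjects.

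**What to change.** - In 7.3.3, replace the repeat-data sentence. For every repeat ablation in the blanking period, the study database should record the date, entrance block for each vein, each target ablated, and for each target whether the study device, a non-study device or manual manipulation was used. For repeats after day 90, date and mode are enough.
- In the general steps of 7.3.3, state that the entrance-block verification and its recording apply to repeats in the blanking period as well as to the initial procedure, in line with what 5.3 already scores.
- For repeats already performed, complete these items from the source records required by 7.13.

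The cost is a few sentences of protocol text and, if the electronic case report form lacks the items, a short repeat-procedure page. Sites would look up past repeats among subjects already enrolled (74 by Table 6). The endpoint definition, hypotheses, performance goals and sample size do not change.
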